2.7.2 Statistical hypothesis, model, and method of analysis

There are no pre-specified hypotheses for secondary endpoints. Model, method of analysis, and handling of missing values/censoring/discontinuations are presented in the following subsections by topic.

2.7.2.1 Analysis of clinical success at timepoints other than 48 hours

The clinical success at hours 24, 72, at hospital discharge, Days 8, 15, 22, and 29 will be evaluated using the FAS and data from all cohorts pooled.

At each visit, 2-sided 90% CIs for the proportion of patients with clinical success for each treatment group will be provided based on the Clopper-Pearson exact method. In addition, 2-sided 90% CIs for the difference between a cipargamin dose regimen and artesunate will be provided using a Mantel-Haenszel estimate of the common risk difference stratified by cohort where Cohorts 1 and 2 will be combined.

Two-sided 90% CIs for the difference for the Mantel-Haenszel estimate of the common risk difference will be calculated using the local lab data only. Descriptive statistics will be provided for Cohorts 1 and 2 using the central lab data.

Intercurrent events and non-intercurrent events that may occur and affect the derivation of clinical success are handled in [Table 2-4](#).

Table 2-4 Handling of other events that may occur and affect the derivation of clinical success at a visit other than 48 hours

Event	During hospital period (hours 24, 72 and at hospital discharge)[§]	After discharge from hospital (Days 8, 15, 22, and 29)
Receive IV antimalarial rescue medication prior to the visit	Not clinical success	Not clinical success
Death not related to malaria (as per adjudication committee)	Not applicable	Use the worst clinical success outcome between the hospital discharge visit and the last available visit
Discontinue the study prior to the visit due to other reasons, such as withdrawal of consent, lost to follow-up, COVID-19, etc.	Not clinical success due to early discharge	Use the worst clinical success outcome between the hospital discharge visit and the last available visit
Skipping the visit	Use the worst clinical success outcome from the visit before or visit after	Use the worst clinical success outcome from the visit before or visit after
Missing parasite assessments with visit	
 • Not clinical success if asexual parasites present in the previous visit • Ignored* otherwise 	
 • Not clinical success if asexual parasites not cleared at the hospital discharge or parasites reappearance in a previous visit • Ignored* otherwise
Altered consciousness: missing Prostration, missing Glasgow Coma Score in adults or missing Blantyre coma score in children	Use the latest visit (including baseline) prior to the visit for each missing item	
 • Not clinical success if prostration or coma is reported as AEs for the visit • Ignored* otherwise
Renal impairment: missing SCr	
 • Not clinical success if Renal Replacement Therapy is used at the visit • Use the latest SCr prior to the visit 	
 • Not clinical success if Renal Replacement Therapy is used at the visit • Not clinical success if renal failure or renal impairment is reported as AE for the visit • Ignored* otherwise
Acidosis and respiratory distress: missing plasma lactate or missing respiratory distress assessment	Use the result from the latest visit prior to the visit for each missing item	
 • Not clinical success if lactic acidosis or respiratory distress is reported as AE for the visit • Ignored* otherwise
[§] Partial data missing is unlikely prior to hospital discharge [*] Patient is considered as clinical success unless the patient does not meet clinical success due to other criterion		

Additional analyses

At each visit, 2-sided 90% CIs for the proportion of patients with clinical success for each treatment group will be provided based on the exact method and 2-sided 90% CIs for treatment difference vs artesunate will be provided using the Wilson uncorrected method by cohort.

For death not related to malaria and discontinuation of study after the hospital discharge, the following 2 sensitivity analyses will be performed:

- Use the last available clinical success outcome prior to death or discontinuation.
- Use multiple imputation methods (see [Appendix 5.8.4](#))

2.7.2.2 Analyses of Individual signs of severe malaria

The following analysis for new severe malaria signs (as per WHO severe malaria criteria) after the IV study treatment will be performed.

The shift table of post-baseline presence relative to baseline presence of Individual signs of severe malaria or not will be provided by visit (24 hours, 48 hours, 72 hours, at hospital discharge, Day 6, Day 8, Day 15, Day 22, and Day 29), cohort, and treatment group. There are 7 individual signs and symptoms of malaria (See [Section 2.1.1](#)). Number and percent of patients with count of 0, 1, 2, 3, 4, 5, 6, and 7 different signs and symptoms by timepoint will be provided for each cohort and treatment group.

For BCS and GCS, individual scores for each category (eye opening, verbal response, motor system) will be listed. Refer to [Appendix 5, Section 5.1](#) for more details.

In order to assess the impact of IV rescue medication, a listing of signs and symptoms of severe malaria over time will be provided for the patients receiving IV rescue.

Analysis will be based on FAS using observed data.

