All analyses described below will be performed using the FAS without imputation for missing assessments, ie., missing assessments will be excluded from analysis.

For the following individual signs of severe malaria, the shift table of post-baseline presence relative to baseline presence or not will be provided by visit (24 hours, 48 hours, 72 hours, 96 hours, at hospital discharge, Day 6, Day 8, Day 15, Day 22, and Day 29), cohort, and treatment group:

- Altered consciousness - Prostration or GCS < 11 for age > 5 yrs / BCS < 3 for age ≤ 5 years
- Renal Impairment- Serum creatinine > 3 x ULN or > 3 mg/dL or need for renal replacement therapy
- Acidosis- Serum lactate > 4 mmol/L
- Respiratory distress – present or absent
- Severe anemia- Hb < 5 g/dl or Hb < 7g/dl in pediatric and adults respectively with parasite count of > 10,000/μl or need of blood transfusion
- Jaundice- Serum bilirubin > 3 g/dl with parasite count of > 100,000/μl
- Hypoglycemia- plasma glucose < 40 mg/dL

Number and percent of participants will be provided by cohort and treatment group for the following events related to severe malaria:

- Convulsion developing or persisting > 6 hour after the IV study treatment. Note: “persisting > 6 hour” means that convulsion is present at baseline and again at a visit that is > 6 hours after IV study treatment.
- New severe malaria signs (as per WHO severe malaria criteria) after the IV study treatment
- Neurological sequelae (by adjudication) at Day 29

Neurological Examination results will be summarized descriptively by visit, cohort, and treatment group.

For the following time to event variables, the first visit with the event will be used to calculate the time if a participant experiences the event. If a participant does not experience the event, the time will be censored at the last visit assessment for specific type of event (such as last sit assessment, etc.) with the exception of date of discontinuation (or death) for time to oral antimalarial therapy.

- Time to oral antimalarial therapy (in hours),
- Time to recover prostration in participants who are prostrated at baseline

Descriptive statistics will be provided using the Kaplan-Meier method and Kaplan-Meier curves will be presented by cohort and treatment.

Day of discharge from hospital will be summarized descriptively by cohort and treatment group. Day of death will be used in case of death during hospitalization.

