- For **height in cm** and **SCr in mg/dL**: $\text{eGFR (ml/min/1.73 m}^2\text{)} = 0.413 \times (\text{height/SCr})$
- For **height in cm** and **SCr in $\mu\text{mol/L}$** : $\text{eGFR (ml/min/1.73 m}^2\text{)} = 36.5 \times (\text{height/SCr})$

Normal renal GFR values, as measured by inulin clearance ([Schwartz and Furth 2007](#)), are provided in [Table 16-4](#) below:

Table 16-4 **Normal GFR in children and young adults, as assessed by inulin clearance (adapted for pediatric participants included in this study)**

Age	Mean GFR \pm SD (ml/min per 1.73 m ²)
Term babies	
4-6 months	87.4 \pm 22.3
7-12 months	96.2 \pm 12.2
1-2 years	105.2 \pm 17.3
Children	
3-4 years	111.2 \pm 18.5
5-6 years	114.1 \pm 18.6
7-8 years	111.3 \pm 18.3
9-10 years	110.0 \pm 21.6
11-12 years	116.4 \pm 18.9
13-15 years	117.2 \pm 16.1
2.7-11.6 years	127.1 \pm 13.5
9-12 years	116.6 \pm 18.1
Young adults	
16.2-34 years	112 \pm 13

16.3

CCI

Table 16-5

CCI

CCI

16.4 Appendix 4: Modified version of WHO classification of signs of severe *P. falciparum* malaria

Severe malaria is defined as occurrence of one or more of the following observations, in the absence of an identified alternative cause, and in the presence of *P. falciparum* asexual parasitemia (WHO 2014)

Table 16-6 Definition of severe malaria

Signs	Definition
Impaired consciousness	A Glasgow Coma Score < 11 in adults or a Blantyre coma score < 3 in children
Prostration	Generalized weakness so that the person is unable to sit, stand or walk without assistance
Multiple convulsions	More than two episodes within 24 hours
Acidosis*	venous plasma lactate ≥ 4 mmol. Severe acidosis manifests clinically as respiratory distress – rapid, deep and laboured breathing
Hypoglycaemia	Blood or plasma glucose < 2.2 mmol (< 40 mg/dL)
Severe malarial anaemia	A haemoglobin concentration < 5 g/dl or a haematocrit of < 15% in children < 12 years of age (< 7 g/dl or < 20%, respectively, in adults) together with a parasite count > 10,000/ μ l
Renal impairment (acute kidney injury)**	Plasma or serum creatinine > 265 μ mol/L (3 mg/dL) or ≥ 3 x ULN or blood urea > 20 mmol/L
Jaundice	Plasma or serum bilirubin > 50 μ mol/L (3 mg/dL) with a parasite count > 100,000/ μ l
Pulmonary edema	Radiologically confirmed, or oxygen saturation < 92% on room air with a respiratory rate > 30/min, often with chest indrawing and crepitations on auscultation

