Key signs of Severe Malaria are Altered consciousness, Renal impairment, Acidosis, and Respiratory distress.

Signs of severe malaria

The following signs of severe malaria will be monitored at every visit during the entire study duration.

- **Altered consciousness** – Prostration (inability to sit or drink or breast feed) or GCS < 11 for patients > 5 years / BCS < 3 for patients ≤ 5 years of age
- **Renal Impairment** - Serum creatinine > 3xULN or > 3 mg/dL or need for renal replacement therapy (RRT)
- **Acidosis** - Plasma lactate > 4 mmol/L or Respiratory distress.
Respiratory distress is defined as rapid, deep and labored breathing (costal indrawing, use of accessory muscles and nasal flaring)- present or absent.
In database, Plasma lactate is captured under lactic acid.
- **Severe anemia** - Hb < 5 g/dl or Hb < 7g/dl in pediatric and adults respectively or need of blood transfusion
- **Jaundice** - Serum bilirubin > 3 mg/dl
- **Hypoglycemia**- plasma glucose < 40 mg/dL
- **Blantyre coma scale (BCS)** is a number from 0 to 5 based on [Appendix 5, Table 5-1](#) for patients ≤ 5 years. The score is determined by adding the results from three categories: Motor response, verbal response, and eye movement. The minimum score is 0 which indicates poor results while the maximum is 5 indicating good results.

- **Glasgow Coma Scale (GCS)** is a clinical scale used to reliably measure a person's level of consciousness for age > 5 years. The score is determined by adding the results from three categories: Motor response, verbal response, and eye movement. A person's GCS score can range from 3 (completely unresponsive) to 15 (responsive) based on [Appendix 5, Table 5-2](#).

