2.7.1 Secondary efficacy endpoints

Secondary efficacy endpoints include:

- Clinical success at 24 hours and 72 hours, hospital discharge Day 6, Day 8, Day 15, Day 22, and Day 29. See [Section 2.1.1](#) for definition of clinical success.
- Individual signs of severe malaria over time
 - Altered consciousness - Prostration or GCS < 11 for patients > 5 years old or BCS < 3 for patients ≤ 5 years old
 - Renal Impairment- Serum creatinine > 3 x ULN or > 3 mg/dL or need for renal replacement therapy
 - Acidosis- Plasma lactate > 4 mmol/L Or Respiratory distress – present or absent

- Severe anemia- Hb < 5 g/dl or Hb < 7g/dl in pediatric and adults respectively with parasite count of > 10,000/μl or need of blood transfusion
- Jaundice- Serum bilirubin > 3 g/dl with parasite count of > 100,000/μl
- Hypoglycemia- plasma glucose < 40 mg/dL
- Proportion of patients with convulsion developing or persisting > 6 hour after start of IV study treatment
- Proportion of patients developing any new severe malaria signs (as per WHO severe malaria criteria) after treatment
- Proportion of patients with neurological sequelae (by adjudication) at Day 29
- Time to oral antimalarial therapy (in hours)
- Time to recover from prostration (in hours) in patients who are prostrated at baseline
- Proportions of patients with $\geq 90\%$ *P. falciparum* asexual parasite reduction from baseline at 24 and 48 hours
- *P. falciparum* asexual parasite reduction ratios (PRR) at 12, 24 and 48 hours
- Time to *P. falciparum* asexual parasite clearance (PCT) (in hours)
- Time to fever clearance (FCT) (in hours)
- PCE slope half-life
- Proportion of patients with recrudescence and reinfection by Day 29

Hospital discharge day will be defined as the visit day where healthcare resource utilization has the hospital discharge date.

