Clinical success is a dichotomous composite (comprised of malaria related death, *P. falciparum* asexual parasites count, and major clinical signs of severe malaria) variable which is derived according to [Section 2.1.1](#) and restated below.

A patient is said to have achieved the clinical success at a given timepoint if the patient did not die either during the initial hospitalization nor due to malaria post the initial hospitalization, shows absence of *P. falciparum* asexual parasites (using local lab for all cohorts and repeated for central lab for Cohorts 1 and 2), and did not have any of the key signs or symptoms of severe malaria on that given timepoint. Note: Deaths occurring post initial hospitalization will be evaluated by designated adjudication committee to confirm if they are related to malaria.

In the current study, Blood film for microscopic counts of *P. falciparum* asexual parasite are collected at screening, pre-dose, Hours 1, 2, 4, 6, 12, 18, 24, 30, 36, 42, 48, 72 (hospital discharge), Days 6, 8, 15, 22, 29, and unscheduled visit. Neurological assessments are performed on screening, pre-dose, Hours 6, 12, 18, 24, 36, 48, 72 (hospital discharge), Days 6, 8, 15, 22, 29, and unscheduled visit. Altered consciousness will be determined using these neurological assessments as defined in [Section 2.1.1](#). Plasma lactate and serum creatinine assessments are performed on screening, Hours 6, 12, 18, 24, 36, 48, 72 (hospital discharge), Days 6, 8, 15, 22, 29, and unscheduled visit. Note: if hospital discharge does not occur at Hour 72 or a scheduled visit, these assessments should be performed at hospital discharge. Renal replacement therapy (RRT) will be captured on concomitant and non-drug therapy CRF page. These assessments are required for determination of renal impairment. Respiratory distress is recorded by investigator in the severe malaria CRF and will also be identified using adverse event pages.

Key signs of Severe Malaria are (a) Altered consciousness, (b) Renal impairment, (c) Acidosis. These signs are defined below.

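### The SAP's analysis of new severe malaria signs derives no patient-level any-new-sign variable and uses a shorter, merged sign list, so it cannot give the proportion that the protocol names

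*SAP*

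**What the plan says.** **Endpoint.** SAP 2.7.1 lists "Proportion of patients developing any new severe malaria signs (as per WHO severe malaria criteria) after treatment". Protocol 12.5.1 places "New severe malaria signs (as per WHO severe malaria criteria) after the IV study treatment" among the events to be reported as number and percent of participants by cohort and treatment group. It stands beside convulsions and neurological sequelae, and apart from the shift table of individual signs.

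**Analysis assigned to it.** SAP 2.7.2.2 states "The following analysis for new severe malaria signs (as per WHO severe malaria criteria) after the IV study treatment will be performed". It then gives a shift table of post-baseline against baseline presence of each sign, "by visit (24 hours, 48 hours, 72 hours, at hospital discharge, Day 6, Day 8, Day 15, Day 22, and Day 29", by cohort and treatment group. It adds a tabulation of patients with 0 to 7 signs at each timepoint. The analysis uses the FAS with observed data.

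**Sign list.** SAP 2.7.2.2 says "There are 7 individual signs and symptoms of malaria" and points to SAP 2.1.1. There, altered consciousness is a single sign: "Prostration (inability to sit or drink or breast feed) or GCS < 11 for patients > 5 years", with the Blantyre score for younger children. Acidosis is lactate above 4 mmol/L or respiratory distress. The others are renal impairment, severe anaemia, jaundice and hypoglycaemia.

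**WHO list.** Protocol 16.4, Table 16-6, has 12 signs. Prostration has its own row, apart from impaired consciousness: "Generalized weakness so that the person is unable to sit, stand or walk without assistance".

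**Examination times.** SAP 5.8.4 says "Neurological assessments are performed on screening, pre-dose, Hours 6, 12, 18, 24, 36, 48, 72 (hospital discharge), Days 6, 8, 15, 22, 29". Protocol Tables 8-1 and 8-2 schedule the other severe malaria examinations at the same post-dose hours in hospital, with a footnote referring to Table 16-6.

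SAP section 4 declares no change from the protocol analyses.

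**The concern.** The endpoint is one yes/no outcome per patient: did any new sign appear after dosing? The analysis the SAP attaches to it is a set of separate tables by sign and visit, on a list that is not the WHO list the endpoint cites. Whoever programs the proportion would have to choose the signs, the visits and the treatment of deaths without a pre-specified rule.

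This matters because IV rescue for clinical decline exists only in the cipargamin arms (Protocol 6.2.1), so rescue use cannot compare worsening between arms. A new-sign proportion can. Individual signs over time are also among the outputs sent to the DMC (SAP Table 2-13). Clinical success is not, unless the review after Cohort 4 becomes an interim analysis.

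**Working it through.** **1. Can the stated outputs give the proportion?** Let N_i = 1 if patient i has at least one sign s absent at baseline and present at some post-dose assessment t. The endpoint is ΣN_i / n. The shift table gives only A(s,t), the number moving from absent to present for one sign at one visit. One patient can appear in several cells, so the tables only bound the total:

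max A(s,t) ≤ ΣN_i ≤ min(n, ΣA(s,t)).

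The 0–7 count does not close the gap. A patient's change in count equals signs gained minus signs lost, so an unchanged count can hide one sign lost and another gained.

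**2. Signs.**

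| Table 16-6 | Protocol 8.3.1.2 | SAP 2.1.1 |
|---|---|---|
| Impaired consciousness; prostration (2 rows) | one sign | one sign |
| Acidosis, including respiratory distress (1 row) | two signs | one sign |
| Renal, anaemia, jaundice, hypoglycaemia (4 rows) | four signs | four signs |
| Multiple convulsions, pulmonary oedema, bleeding, shock, hyperparasitaemia (5 rows) | none | none |
| Total: 2 + 1 + 4 + 5 = 12 | 1 + 2 + 4 = **7** | 1 + 1 + 4 = **6** |

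The SAP's figure of 7 is reproduced only on the Protocol 8.3.1.2 list. The section the SAP cites holds 6; its further Blantyre and Glasgow bullets are scales, not signs. Convulsions are analysed separately in SAP 2.7.2.3. Table 16-6 itself keeps respiratory distress within the acidosis row, so the case for separating it from lactate rests on Protocol 8.3.1.2.

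**3. Times.** The scheduled in-hospital post-dose examinations are at 6, 12, 18, 24, 36, 48 and 72 h, seven in all. The shift table uses 24, 48 and 72 h (plus discharge), so 7 − 3 = 4 are left out: 6, 12, 18 and 36 h. SAP Table 5-9 nevertheless defines severe-malaria analysis windows for those four.

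**4. What happens to particular patients.**
- Prostrate but awake at baseline, in coma at 24 h: present to present, no new sign. Cohort 1 enrols on prostration and/or repeated vomiting without other severe signs (Protocol 5.1), so this applies to every Cohort 1 patient who enters prostrate.
- Lactate above 4 mmol/L at baseline, respiratory distress later: present to present under SAP 2.1.1, absent to present under Protocol 8.3.1.2.
- New shock, pulmonary oedema, significant bleeding or hyperparasitaemia: no row in the table.
- Sign at 12 h, gone by 24 h, or seen only at 36 h: no entry. A sign at 12 h that persists to 24 h is captured.
- Death before 24 h: with observed data, no post-baseline entry.

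**5. Size.** Neither document gives the frequency or timing of new signs. As an illustration on assumed values only, let m be the share of new-sign events in omitted signs, c the share that is masked prostration-to-coma, and t the share of the rest that is transient between shift visits. Then share missed = m + c + (1 − m − c)t. Taking m and c at 5%, 15% or 30% and t at 5%, 25% or 50%:
- lowest: 0.05 + 0.05 + 0.90 × 0.05 = 0.145
- highest: 0.30 + 0.30 + 0.40 × 0.50 = 0.80
- above one half in 15 of the 27 combinations.

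The range is too wide to support any statement about how much is missed.

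**The case against.** The strongest reply is that the proportion is planned and only its derivation is unstated. SAP 2.7 promises n and percent for categorical secondary endpoints by group and cohort, and pooled. SAP 2.7.1 names this endpoint by WHO criteria, SAP 2.1 ties the analysis to Protocol section 12, and section 4 reports no change. The 0–7 count is given by timepoint and is not expressly confined to the shift-table visits. On the Protocol 8.3.1.2 list the figure of seven is correct and the lactate masking disappears. The item is also absent from the objectives tables, carries no hypothesis and is descriptive.

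Much of this stands as to weight. It does not repair the rule. The general sentence supplies no sign list, visits or handling of death, and the only list SAP 2.7.2.2 points to is the short one in 2.1.1.

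The reply is right about other outputs. A reader might infer that this is the only measure of on-treatment worsening besides death and rescue, or that progression from prostration to coma cannot be seen at all. The documents do not support either. Adverse events are tabulated by severity and separately for the IV period (SAP 2.8.1). Laboratory shifts use each visit and the worst value, lactate shifts are given at each visit (2.8.2), and newly notable vital signs are counted (2.8.3.2). Coma-score components are listed (2.7.2.2), and clinical success is assessed at 24, 48 and 72 h. These still do not replace the endpoint. Adverse events are coded by preferred term, not derived from Table 16-6, and the listing of signs in rescued patients can contain only cipargamin patients.

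**Conclusion.** The point holds. Followed as written, SAP 2.7.2.2 does not deliver the secondary proportion named in Protocol 12.5.1 and SAP 2.7.1. Its list omits five of 12 Table 16-6 signs and merges two more into one, its shift table leaves out four of seven in-hospital examination times, and its stated seven signs do not match the six in the section it cites.

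A reader might go further and infer that most deterioration is scored as no new sign, or that a dose allowing early worsening would look equal to artesunate. Neither follows. The share missed is not given, persistent early signs are captured, the same rule applies to both arms, and the other outputs would show part of the worsening. The conclusion rests on reading the SAP literally. The primary analysis is unaffected, and so is clinical success at 48 h, where any key sign present counts as failure whether or not it is new. The SAP should be changed before database lock.

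**What to change.** In SAP 2.7.2.2, derive one indicator per patient: any Table 16-6 sign absent at baseline and present at any post-dose assessment at which that sign was assessed, scheduled or unscheduled.

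- Score prostration and coma separately, and lactate and respiratory distress separately.
- Keep the transfusion and renal-replacement triggers of SAP 2.1.1, which Table 16-6 lacks. State which anaemia and jaundice definition applies, since SAP 2.1.1 drops the parasite-count condition that SAP 2.7.1 and Table 16-6 carry.
- Report n (%) by arm and cohort, and for the pooled cohorts.
- Show deaths without a later assessment as a separate row. Give new sign or death as a supplementary composite, so that the endpoint itself is not redefined.
- Keep the shift table as description, and align its sign list and the 0–7 count with Protocol 8.3.1.2.

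The cost is SAP wording and a little programming. No visit is added, because the examinations are already scheduled against Table 16-6 and recorded in the database. One limit should be stated with the result: laboratory-based signs are not scheduled at every examination. Table 8-1 has no point-of-care chemistry or haematology at 18 h, and no hepatic panel or haematology at 6 h.

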8.3.1.2 Signs of severe malaria

Participants will be monitored for the presence of the following signs of severe malaria during the entire study duration:

- Altered consciousness - Prostration or GCS < 11 for participants > 5 years / BCS < 3 for participants ≤ 5 years of age
- Renal Impairment - Serum creatinine > 3xULN or > 3 mg/dL or need for renal replacement therapy
- Acidosis - Serum lactate > 4 mmol/L
- Respiratory distress - present or absent
- Severe anemia - Hb < 5 g/dl or Hb < 7g/dl in pediatric and adults respectively or need of blood transfusion
- Jaundice - Serum bilirubin > 3 g/dl
- Hypoglycemia- plasma glucose < 40 mg/dL

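### The SAP merges respiratory distress into acidosis, which leaves six individual signs, yet states seven and plans a 0–7 count; the protocol lists the two signs separately

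*SAP*

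**What the plan says.** **Protocol.** Section 8.3.1.2 lists seven signs to be monitored: altered consciousness, renal impairment, acidosis, respiratory distress, severe anemia, jaundice and hypoglycemia. Acidosis is defined there by lactate above 4 mmol/L alone, and respiratory distress is a separate entry: "Respiratory distress - present or absent". Section 12.5.1 repeats the same seven and asks for a shift table of post-baseline against baseline presence for them, again with "Respiratory distress – present or absent" as its own item.

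**SAP.** In Section 2.1.1 the acidosis entry in the list of signs reads "Plasma lactate > 4 mmol/L or Respiratory distress", and respiratory distress has no entry of its own in that list. Section 2.7.1 does the same: "Acidosis- Plasma lactate > 4 mmol/L Or Respiratory distress – present or absent". Section 2.7.2.2 then says "There are 7 individual signs and symptoms of malaria", points to 2.1.1, and asks for "Number and percent of patients with count of 0, 1, 2, 3, 4, 5, 6, and 7 different signs and symptoms by timepoint", for each cohort and treatment group. Section 4 records no change to the protocol-specified analyses.

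**The concern.** The proportion of participants with individual signs of severe malaria over time is a protocol secondary endpoint. Protocol 8.3.3 relies on the individual assessment of symptoms for an in-depth look at efficacy. SAP Table 2-13 marks this output as provided both for the interim assessment after Cohort 2 and for the DMC review after Cohort 4. Clinical success is not provided at the former, and at the latter only if that review is upgraded to an interim analysis.

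The SAP's number of signs and its list of signs do not agree with each other, and the list does not agree with the protocol. A programmer following the SAP has to choose an interpretation. The choice determines whether respiratory distress has a row, what the acidosis row means, and what the count contains.

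**Working it through.** **Step 1: reproduce the figure of seven.** Counting entries in each list:

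| Source | Distinct signs | Acidosis | Respiratory distress |
|---|---|---|---|
| Protocol 8.3.1.2 and 12.5.1 | 7 | lactate > 4 only | own sign |
| SAP 2.7.1 | 6 | lactate > 4 or respiratory distress | inside acidosis |
| SAP 2.1.1 | 6 | lactate > 4 or respiratory distress | inside acidosis |

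SAP 2.1.1 has eight bullets, because it also describes the Blantyre and Glasgow scales. Taking the two scales as one age-specific item gives seven, but the coma score is already part of altered consciousness, so this repeats a sign and still leaves respiratory distress without a row. The stated seven is therefore not reproduced from the section it cites.

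**Step 2: write the count under each reading.** Let L = 1 if lactate is above 4 mmol/L, R = 1 if respiratory distress is present, and B = the number present among the other five signs (0 to 5).

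- Protocol's seven signs: B + L + R, range 0 to 7.
- SAP, six signs as listed: B + max(L, R), range 0 to 6. The row for 7 is always empty.
- SAP, respiratory distress added as a seventh sign beside merged acidosis: B + max(L, R) + R, range 0 to 7, with overlap.

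**Step 3: compare them**, with B = 0:

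| Lactate > 4 | Respiratory distress | Protocol's signs | SAP six | SAP seven with overlap |
|---|---|---|---|---|
| no | no | 0 | 0 | 0 |
| yes | no | 1 | 1 | 1 |
| no | yes | 1 | 1 | **2** |
| yes | yes | 2 | **1** | 2 |

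The six-sign reading minus the protocol list is max(L, R) − L − R, which is −1 only when L = R = 1. The overlapping reading minus the protocol list is max(L, R) − L, which is +1 only when R = 1 and L = 0.

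Of the 2^7 = 128 presence/absence patterns, 64 include respiratory distress. Each SAP reading departs from the protocol list in 2^5 = 32 of them, a different 32 in each case. These are logical patterns, not patient frequencies.

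**Step 4: the shift table.** Under either SAP reading, a patient with respiratory distress and lactate of 4 or below is acidosis-positive. Under Protocol 12.5.1 the same patient is acidosis-negative and positive for respiratory distress. With the six signs as listed, no respiratory-distress shift is produced.

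**Step 5: does the rest of the SAP settle the reading?** It does not. Section 2.1.1 elsewhere says "Key signs of Severe Malaria are Altered consciousness, Renal impairment, Acidosis, and Respiratory distress". Appendix 5.8.4 gives three key signs, with respiratory distress inside acidosis, then lists respiratory distress separately among the candidate imputation variables and omits it from the description of the input data set.

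**The case against.** The strongest reply is that this is a drafting slip with an evident intention. The merged definition comes from the protocol itself: Table 8-3 puts respiratory distress under acidosis for clinical success. The SAP also names respiratory distress beside acidosis as a key sign, and the stated total of seven matches the protocol. The outputs are descriptive, on observed data, with no hypothesis attached. That stands as to intention and weight. It does not make the list in 2.1.1, the endpoint in 2.7.1 and the count in 2.7.2.2 agree.

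A reader might also infer more than the documents support:

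- *That no lactate-only shift is planned.* SAP 2.8.2 plans one by visit, cohort and treatment group. It uses the safety set rather than the FAS and a top category of 4 mmol/L or above rather than above 4, so it is close to the protocol's acidosis shift but not the same.
- *That every patient with respiratory distress is miscounted.* Each reading is off for one subset only, as Step 3 shows.
- *That a protocol-defined score is violated.* The protocol asks for a shift table of the signs; the 0–7 count is a SAP addition. The comparison here is with a count of the protocol's seven signs.
- *That the SAP instructs double counting.* It does not. The overlap arises only if a programmer reaches seven by adding respiratory distress while leaving it inside acidosis.

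**Conclusion.** The point holds for the individual-sign shift table and the sign-count table. The SAP's list has six distinct signs, its text claims seven, and the protocol's seven are defined differently, with no change declared. As written, the respiratory-distress shift is missing and the acidosis row mixes two findings. The count is out by one for one subset of patients with respiratory distress: too low when lactate is above 4 under the six-sign reading, or too high when lactate is 4 or below under the overlapping seven-sign reading.

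The number of patients affected cannot be given. The documents state neither the prevalence of respiratory distress at the tabulated visits nor its overlap with raised lactate, so no percentage is offered.

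Clinical success should not be read as affected by the merger: either finding alone makes a patient a failure, whether the two are merged or separate. The primary endpoint uses parasite counts and is also untouched. The conclusion rests only on the definitions as printed. It should be corrected because the output is a secondary endpoint that goes to the interim assessment and the DMC, but it threatens no inferential result.

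**What to change.** For the individual-sign shift tables and counts, in SAP 2.1.1, 2.7.1 and 2.7.2.2:

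- define acidosis as plasma lactate above 4 mmol/L only;
- list respiratory distress (present/absent) as the seventh sign, as in Protocol 8.3.1.2 and 12.5.1;
- keep the combined definition only for the clinical-success key sign, and say so.

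The list then has seven non-overlapping signs and the 0–7 count works as stated. If the merged sign is preferred, state six signs, plan a 0–6 count, and declare the departure from the protocol in SAP Section 4.

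The cost is SAP wording and the matching table shells and programs. Appendix 5.8.4 indicates that lactate comes from the point-of-care device or local laboratory and respiratory distress from the severe malaria CRF, so no new data are needed.
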